5.1 Variables

The following pharmacokinetic parameters will be determined for free CFZ533 in plasma (i) Ctrough or Cmin, and Cmax will be directly derived from the bioanalytical data and listings, and (ii) AUClast from the last dose at Day 141 will be determined using the actual recorded

sampling times and non-compartmental methods with Phoenix WinNonlin (Version 8.0 or higher). The linear trapezoidal rule will be used for AUClast calculation.

The pharmacokinetics of CFZ533 is non-linear and characterized by target-mediated disposition where CD40 binding by CFZ533 is leading to CFZ533 elimination (this includes receptor-mediated endocytosis by the membrane bound CD40, and subsequent metabolism of the CFZ533-CD40 complexes). As such, it is expected that:

- The amount of drug-target complex does influence the pharmacokinetics of CFZ533,
- Tissue metabolism may have a significant impact on the disposition of CFZ533 (the volume of distribution will be dependent on clearance),
- The volume of distribution may not be accurately inferred from plasma concentration alone, and the values for the volume of distribution obtained from a non-compartmental analysis (NCA) may be incorrect,
- Volume of distribution and clearance parameters (as inferred from NCA analysis) would decrease when the dose increases.

The NCA approach is not appropriate due to violations of the assumptions that the disposition of the drug is linear, and that the elimination is from sites that are in rapid equilibrium with blood, therefore secondary PK parameters (e.g. clearance, volume of distribution or terminal elimination half-life) will not be determined in this study

For each PK and total soluble CD40 samples, the actual recorded sampling time will be captured, and the elapsed time since the first and since the last dose before sample collection will be calculated. PK samples which are collected +/- 30% of the scheduled post-dose timepoint will be excluded from the summary statistics.

5.2 Descriptive analyses

Commercially Confidential Information

5.2.1 Graphical presentation of results

Arithmetic mean (SD) profiles will be generated along with overlaying individual plasma concentration-time profiles and individual plasma concentration-time profiles.

5.3 Pharmacokinetic/pharmacodynamics interactions

PK/PD analysis (e.g. incl. free CFZ533 and total soluble CD40 in plasma) may be explored graphically. Modeling of PK/PD data using a population approach may be performed as appropriate and will be reported if necessary in a separate, standalone modeling and simulation report.

6 Statistical methods for Pharmacodynamic (PD) parameters

Baseline is defined as the last available value prior to dosing and will include Screening if no other value after Screening is available.

For UPCR and UACR where the analyses are split between first morning void and clinic spot samples then the last available value prior to dosing from the first morning void or clinic spot sample respectively will be used. For the analyses that use the first morning void when available and the clinic spot sample if it is not available then the last available first morning void prior to dosing will be used as the baseline, if there are no first morning void values available prior to dosing then the last available clinic spot sample prior to dosing will be used as the baseline for these analyses.

Summary of key estimands for efficacy

Estimands are defined for this trial to address the efficacy objectives of the trial and to provide supportive evidence for those objectives. These estimands are defined in detail in the subsequent sections and are summarized in Table 6-1. The analysis for other safety/efficacy/PK data are described in other sections of this SAP.

Table 6-1 Summary of key estimands

	Estimand	Variable estimand is based on	Section
P1	Primary 1 – renal proteinuria	Ratio from baseline in urinary protein creatinine ratio (UPCR) at Week 25	6.1
S2	Secondary 1 - renal	Proportion with complete renal remission (CRR)	6.2

6.1 Primary estimand 1

The primary estimand 1 addresses the second primary objective:

- To assess the effect of CFZ533 on renal proteinuria in moderately active lupus nephritis patients after 24 weeks of treatment as an add-on therapy to standard of care as compared to placebo.

This estimand addresses the scientific question of whether treatment with CFZ533 reduces UPCR in moderately active lupus nephritis patients after 24 weeks of treatment without death, rescue medication and treatment discontinuation as an add-on therapy to standard of care.

6.1.1 Definition of primary estimand 1: UPCR

- Population: moderately active proliferative lupus nephritis patients.
- Variable: Ratio from baseline in UPCR at Week 25
- Treatment: CFZ+SOC, Placebo+SOC
- Summary Measure: Ratio of Geometric Means of CFZ533 versus placebo.

Hypothetical strategy will be used to deal with death, rescue medication and treatment discontinuation inter-current events. Data from patients taking rescue medication during the trial (or failing to tolerate steroid taper, for patients receiving oral corticosteroid at baseline) will be excluded from the date of rescue medication intake or failure of the steroid taper. Data from patients who discontinue study treatment will also be excluded, from the date of study drug discontinuation. A medical assessment prior to database lock will determine which patients are deemed to have failed the steroid taper based on clinical relevance of the steroid dose taken and the potential impact on the primary endpoint.

No other inter-current events will be taken into account in the estimand.

Commercially Confidential Information

Statistical analysis model

The ratio from baseline in UPCR will be log transformed prior to the analysis. A repeated measures model will be fitted with factors for treatment group (CFZ533 or placebo) and visit (e.g. Week 5, 9, 13 etc.). The model will also include a factor for the prednisone dose-equivalent at baseline (≤ 10 mg, > 10 mg) based on the concomitant medication information in the database rather than the stratification factor from the randomization. Log-transformed baseline UPCR will be included in the model as a covariate along with the interactions between visit and all of the fixed effects and the log-transformed baseline by visit interaction. A normal errors model will be assumed with an unstructured covariance matrix to account for the correlation within subjects. The model will be estimated using maximum likelihood techniques. If there are values of 0 then 0.1 will be added to all the UPCR data prior to the log transformation.

At each of the visits, the difference between the CFZ533 and placebo group will be estimated (along with its corresponding 95% confidence interval) and then back-transformed to provide an estimate of the ratio between treatment groups.

Sensitivity analyses will be considered if a substantial proportion of patients (i.e. more than 15%) receive rescue medicine or discontinue from study treatment. Multiple imputation models may be used to assess the robustness of the missing at random assumption of the primary analysis.

In addition if more than 15% of patients fail to tolerate the steroid taper scheme, a supportive analysis of efficacy using time to lack of taper as endpoint will be conducted. Additional analyses including all patients regardless of their adherence to treatment will be performed.

The adequacy of the model will be assessed by inspecting residual plots.

Data will be listed by treatment and timepoint. Descriptive summary statistics will include mean (arithmetic and geometric), SD, and CV (arithmetic and geometric), median, minimum and maximum and will be presented by treatment and timepoint. Outputs will be provided for the raw UPCR values and also the ratio from baseline. An additional summary will also be provided by baseline steroid dose and also for subjects with biopsies within 2 years prior to randomization and 5 years prior to randomization separately.

Geometric mean (95% CI) of ratio from baseline profiles will be presented along with geometric mean ratio to placebo profiles. These figures will use the data obtained from the above model. Additional profiles of geometric mean (SE) UPCR data will be presented based on the raw data. For these plots the data will be log transformed and the mean and standard error calculated, the standard error will be added/subtracted from the mean on the log scale and then back transformed to obtain the error bars for the plot.

The above outputs will also cover the outputs needed for the secondary objective to assess UPCR at different timepoints.

The above analyses will also be repeated using only the data from the first morning void and clinic spot sample separately.

6.2 Secondary estimand 1

The secondary estimand 1 addresses the secondary objective:

- To assess the effect of CFZ533 on relevant renal outcomes at different time points.

This estimand addresses the scientific question of whether treatment with CFZ533 has a beneficial effect on renal outcomes at different timepoints without death, rescue medication and treatment discontinuation as an add-on therapy to standard of care.

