6.4 Treatment blinding

This is a subject and investigator-blinded study. Subjects and investigators will remain blinded to study treatment throughout the study, except where indicated below.

The identity of the treatments will be concealed by the use of study drugs that are all identical in packaging, labeling, schedule of administration, appearance, and odor.

Site staff

All site staff (including study investigator and study nurse) will be blinded to study treatment throughout the study.

Unblinding a single subject at site for safety reasons (necessary for subject management) will occur via an emergency system in place at the site (see [Section 6.7](#)).

Sponsor staff or delegate

The following unblinded sponsor roles are required for this study amend as appropriate:

Unblinded sample analysts for PK, PD and IG.

The sample analysts will receive a copy of the randomization schedule (via request to the Randomization Office), to facilitate analysis of the samples. The sample analysts will provide the sample data to the study team under blinded conditions unless otherwise allowed.

The study statistician will be able to access the randomization list for interim analyses and is allowed to share unblinded information with the rest of the clinical team as appropriate for internal decision purposes, as outlined in [Section 6.4](#). For example, unblinded summaries and unblinded individual data can be shared with the team for interim analyses.

Study programmers and other personnel involved in study data analysis (e.g. biomarker expert) are allowed to access treatment assignment information for the purpose of conducting interim analyses.

The clinical trial team is allowed to share unblinded results with other sponsor staff (e.g. decision boards) as required for internal decision making on the study or the project at the time of interim analyses while the study is ongoing.

All unblinded personnel will otherwise keep randomization lists and data or information that could unblind other study team members confidential and secure except as described above.

Following final database lock all roles may be considered unblinded.

Table 6-2 Blinding and unblinding plan

Role	Randomization list generated	Treatment allocation & dosing	Safety event (single subject unblinded)	Interim Analysis
Subjects/Patients	B	B	UI	B
Site staff	B	B	UI	B
Drug Supply and Randomization Office	UI	UI	UI	UI
Statistician/statistical programmer/ data analysts (e.g. PK)	B	B	UI	UI

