Independent committees used for assessing interim results, if required (e.g. DMC)	B	B	UI	UI
All other sponsor staff not identified above (trial team, project team, management & decision boards, support functions)	B	B	UI	UI

Key:

UI: Allowed to be unblinded on individual patient level

B: Remains blinded

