8.5 Efficacy / Pharmacodynamics

Pharmacodynamic (PD) samples will be collected at the timepoints defined in the [Assessment schedule](#). Follow instructions outlined in the Site Operations Manual regarding sample collection, numbering, processing and shipment.

In order to better define the PD profile, the timing of the sample collection may be altered based on emergent data. The number of samples/blood draws and total blood volume collected will not exceed those stated in the protocol. The results of the sample analyses needs to remain blinded during the study.

Generally, PD samples will be obtained and evaluated in all subjects, including the placebo group.

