10.5 Adjudication Committee

Not required.

11 Data analysis

The analysis will be conducted on all subject data at the time the trial ends. Any data analysis carried out independently by the investigator should be submitted to Novartis before publication or presentation.

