11.4.3 Handling of missing values/censoring/discontinuations

Data from patients taking rescue medication during the trial (or failing to tolerate steroid taper, for patients receiving oral corticosteroid at baseline) will be excluded from the date of rescue medication intake. Data from patients who discontinue study treatment will also be excluded, from the date of study drug discontinuation. The primary analysis is unbiased under the assumption that the missing data are missing at random (MAR).

If the UPCR from the first morning void sample is not available, then the UPCR from the corresponding spot sample taken at the investigator site will be used in the analyses.

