11.7 Sample size calculation

The sample size is based on the number of patients required to meet the efficacy criteria comparing CFZ533 to placebo in the primary analysis of the ratio from baseline in UPCR at Week 25. The efficacy criteria are:

- Statistically significant decrease in UPCR at week 25 of the treatment period compared to placebo (at the one-sided 10% level)
- Estimated mean reduction in UPCR at week 25 of at least 20% more than on placebo (i.e. ratio of UPCR for CFZ533:placebo ≤ 0.80 or equivalently difference in log UPCR for CFZ533 – placebo ≤ -0.223).

With complete data from 51 patients (34 patients on CFZ533 and 17 patients on placebo), there will be approximately 80% power to achieve the efficacy criteria assuming a true reduction of 36% in UPCR on CFZ533 treatment compared to placebo. This calculation assumes that the standard deviation of the change from baseline in UPCR at 24 weeks is 0.7.

In order to account for a dropout rate of 15%, approximately 60 patients will be enrolled (40 patients on CFZ533 and 20 patients on placebo).

The sample size will be re-assessed based on interim analysis performed approx. 1 to 3 months before the completion of enrollment of 60 patients. The sample size may be increased based on the results of the analysis, up to a maximum of 75 randomized patients.

The sample size calculations were performed using a custom-made R package run in R version 2.13.0.

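### SAP 6.1.1 lets a pre-lock medical judgement remove primary UPCR data as taper failure, and no visible text requires the assessors to be blind to arm and post-baseline UPCR

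*SAP*

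**What the plan says.** SAP 6.1.1 uses a hypothetical strategy for death, rescue medication and treatment discontinuation. For patients on oral corticosteroids at baseline, failing the taper is treated like rescue: UPCR data "will be excluded from the date of rescue medication intake or failure of the steroid taper". Who has failed is settled by a medical assessment before lock. It decides who is "deemed to have failed the steroid taper based on clinical relevance of the steroid dose taken and the potential impact on the primary endpoint". The visible paragraph does not say who assesses, what they may see or whether they are blind. A redacted block follows.

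Protocol 11.4.3 also names taper failure as a reason for exclusion, and data "will be excluded from the date of rescue medication intake". Its visible text does not describe how failure is decided.

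On blinding, Protocol 6.4 says that "unblinded summaries and unblinded individual data can be shared with the team for interim analyses". In Table 6-2 the row "All other sponsor staff not identified above (trial team, project team, management & decision boards, support functions" is marked as allowed to be unblinded at patient level in the interim column. Subjects and site staff stay blinded there. Protocol 6.4 also tells unblinded personnel to keep such information confidential, apart from the sharing it has just described.

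On timing, Protocol 11.7 places the sample-size "interim analysis performed approx. 1 to 3 months before the completion of enrollment of 60 patients", and section 11 opens with "The analysis will be conducted on all subject data at the time the trial ends". Protocol 8.5 adds, for pharmacodynamic samples, "The results of the sample analyses needs to remain blinded during the study". Protocol 10.3 releases the treatment codes after lock.

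**The concern.** The taper-failure decision determines which UPCR values enter the primary analysis, and it is a judgement with no stated dose or duration threshold. Such a decision is safe if the people making it cannot know the arm or the outcome. Making it before lock does not ensure this, because the protocol permits some of the staff who might make it to see individual allocations earlier.

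Two kinds of knowledge matter separately. Assessors who know both arm and UPCR could, even unintentionally, shift the result in either direction. Assessors who are blind to arm but see UPCR would not inflate the false-positive rate much. They could still remove the worst values, which sit mostly in the worse arm, and so dilute a real effect.

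The Protocol 11.7 efficacy criteria rest on this one estimate in a small trial.

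**Working it through.** **Plan's own figure.** Inputs from Protocol 11.7: 34 and 17 complete patients, SD 0.7 (taken as log scale), one-sided 10% level, true ratio 0.64.

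- SE = 0.7 × √(1/34 + 1/17) = 0.208.
- Significance needs a log difference below −1.2816 × 0.2079 = −0.266, a ratio of 0.766. This is stricter than the second criterion (ratio ≤ 0.80), so it decides.
- Power = Φ((0.446 − 0.266)/0.208) = 0.806, which agrees with the stated 80%.

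**One call, by hand.** Take a patient 1.5 SD above the arm mean at Week 25: 1.5 × 0.7 = 1.05 log units. Removing one value d above the mean of n lowers that mean by d/(n − 1). Using Week 25 data alone:

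- Placebo: 1.05/16 = 0.066, so the ratio is multiplied by exp(0.066) = 1.07.
- CFZ533: 1.05/33 = 0.032, so the ratio is multiplied by exp(−0.032) = 0.97.

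**One call, in the planned type of model.** The repeated-measures model keeps the patient's earlier visits, which softens the shift. Assumptions not in the documents: six visits; within-patient correlation 0.6 (compound symmetry) or 0.8 (autoregressive); the patient nearest +1.05 removed from Week 17; 3,000 simulated trials per setting.

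| Call on | Ratio multiplied by | Shift in SEs | Change of verdict at true 0.64 |
|---|---|---|---|
| Placebo patient | 1.032 to 1.047 | 0.15 to 0.22 | met to not met, 4.6 to 7.1% of trials |
| CFZ533 patient | 0.984 to 0.977 | 0.08 to 0.11 | not met to met, 2.6 to 3.3% of trials |

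With no true effect, one CFZ533 call adds about 2 to 3 percentage points to a base rate of about 11%.

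**Blind to arm but not to UPCR.** Week 25 complete cases, with the three highest values of 51 removed: type I error stays near 0.10, but a true 0.64 is estimated as 0.70 and power falls from 0.80 to 0.70. Both kinds of blinding are therefore needed.

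**Timing.** If lock follows the Day 337 visit of the last of 60 patients, the interim precedes it by 1 to 3 months plus 336 days (about 11 months), so about 12 to 14 months.

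**Same-day void.** Protocol 8.5.2 has the first morning void collected at home and a spot sample taken at the site. If an event is dated to a visit day, an exclusion that includes that date drops a value obtained before the event. The simulation had 100,000 patients per arm and a true ratio of 0.64. It assumed 20% placebo events, prompted by a clinical signal correlated 0.5 to 0.7 with UPCR:

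- No events on visit days: 0.64.
- Half on visit days: 0.64 to 0.65.
- All on visit days: 0.65 to 0.67.
- No true effect, all on visit days: 1.00.

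Over 10 to 30% placebo events and correlations 0.3 to 0.7, the extremes are 0.66 (half) and 0.68 (all).

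**The case against.** The strongest reply is that this is an absence in a heavily redacted text. A review procedure could sit in Protocol 3.5, 10.3, 11.4.5 or 11.9, in SAP sections 2 and 3, or in the block inside 6.1.1 itself. That stands: only the visible text can be faulted, and a cross-reference would then be enough.

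A reader might infer that the taper assessors will be unblinded, or that the trial team's blinding ends at the interim. The documents do not support this. Table 6-2 gives permission only. The confidentiality sentence in Protocol 6.4 narrows that permission, although it exempts the interim sharing. Nothing says that the assessors come from the unblinded group.

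A reader might also infer that the SAP tells assessors to consult the patient's UPCR. Impact described as potential more naturally means what the steroid dose could be expected to do. The Protocol 8.5 sentence points the same way, but it does not mention this review, and Protocol 7.2 has proteinuria acted on during the study. The wording leaves the door open; it does not direct anyone through it.

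The size calculation is a constructed case: a high-UPCR patient is picked and assumed to be called a failure. Only patients on oral corticosteroids at baseline can fail the taper, and the simulation did not impose that. A placebo call works against the drug.

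SAP 6.1.1 also plans additional analyses of all patients regardless of adherence. These would expose a result that depends on the calls, and they deserve credit. They do not protect the primary estimate.

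**Conclusion.** The point holds as a missing safeguard in the visible text, not as evidence that the review will be unblinded or that the result will be biased. The primary exclusion rests on a judgement whose assessors are not visibly required to be blind to arm and outcome, in a protocol that permits patient-level unblinding well before lock.

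One call on a high-UPCR patient shifts the ratio by about 2% (CFZ533) or 3 to 5% (placebo), under the assumed visits and correlations. How many calls will arise is not stated.

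The same-day void is a valid but very small correction. A reader might take it for a material bias. The estimate moves from 0.64 to about 0.64 to 0.65 if half of events fall on visit days, and there is no bias under no effect. Because UPCR is a central-laboratory result, the discarded value would rarely have prompted the event.

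Severity: minor to should-fix. Confidence: moderate, limited by the redactions.

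**What to change.** **Main change, SAP 6.1.1.** State that the taper-failure review is completed, documented and frozen before lock by staff who have had no interim unblinding and who see neither arm nor post-baseline UPCR, using only recorded steroid doses, dates and reasons. Reword the second criterion as the expected effect of the steroid dose and its timing. If redacted text already says this, refer to it here.

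**Minor change, SAP 6.1.1 and Protocol 11.4.3.** Keep the home first morning void collected on the event date and exclude data after that date. A same-day clinic spot sample should stay excluded unless it is documented as taken before the event, because Protocol 6.11 asks for medication dates, not times.

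**Cost.** One blinding sentence and one reworded criterion in the SAP, and one drafting change to the exclusion date in each document. Sample size and planned power are unchanged, and no new data are needed. The downside is that a blind reviewer has slightly less clinical context. The change must be in place before the review is done.
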